7	Management and reporting of adverse events/adverse reactions.....	27
8	Plans for disseminating and communicating study results	28
9	References.....	29
	Annex 1. List of stand-alone documents.....	30
	Annex 2. ENCePP checklist for study protocols	31
	Annex 3. Additional information	37
	Annex 3.1. Members of Scientific Medical and Advisory Council	37
	Annex 3.2. Drug relationship [18].....	38
	Annex 4. Designated Medical Event (DME) list	40

List of abbreviations

Abbreviation	Definition
ADR	Adverse Drug Reaction
AE	Adverse Event
AT	As Treated
AS	Active Surveillance
ATC	Anatomical Therapeutic Chemical
ART	Assisted Reproductive Technology
CATI	Computer-Assisted Telephone Interviews
CI	Confidence Interval
CIOMS	Council for International Organizations of Medical Sciences
CFR	Code of Federal Regulations
CRO	Contract Research Organization
CRF	Case Report Form
DME	Designated Medical Events
DMP	Data Management Plan
DVP	Data Validation Plan
DYD	Dydrogesterone
EC	Ethics Committee
eCRF	Electronic Case Report Form
EDC	Electronic Data Capture
EDD	Estimated Date of Delivery
EMA	European Medicines Agency
ENCePP	European Network of Centres for Pharmacoepidemiology and Pharmacovigilance
ePRO	Electronic Patient Reported Outcome
EU	European Union
FDA	Food and Drug Administration
FPI	First Patient In
FU	Follow-Up
GEP	Good Epidemiological Practice
GVP	Good Pharmacovigilance Practice
GPP	Good Pharmacoepidemiology Practices
HATC	Herbal Anatomical Therapeutic Chemical
HCP	Health Care Practitioner
ICF	Informed Consent Form
ICMJE	International Committee of Medical Journal Editors
IEC	Independent Ethics Committee

IRB	Institutional Review Board
IVF	In-Vitro Fertilization
LTFU	Lost To Follow-Up
LPS	Luteal Phase Support
MAH	Marketing Authorization Holder
MedDRA	Medical Dictionary for Regulatory Activities
MM	Major Malformation
NC-FET	Natural Cycle Frozen Embryo Transfer
NIS	Non-Interventional Study
OPRI	Other Pharmacovigilance Relevant Information
OTC	Over-The-Counter
OR	Odds Ratio
PEARLY	Maternal and Newborn Safety profile of Progestogens in EARLY pregnancy
PII	Personal Identifiable Information
PT	Preferred Term
QRP	Quality Review Plan
RECORD	Reporting of studies Conducted using Observational Routinely collected health Data
REOS	Regular End Of Study
SADR	Serious Adverse Drug Reaction
SAP	Statistical Analysis Plan
SES	Socio-Economic Status
SMAC	Scientific and Medical Advisory Council
SMP	Safety Management Plan
SmPC	Summary of Product Characteristics
SOP	Standard Operating Procedures
STROBE	Strengthening the Reporting of Observational studies in Epidemiology
US	United States of America
WHO	World Health Organization
ZEG	Berlin Center for Epidemiology and Health Research (Acronym for “Zentrum fuer Epidemiologie und Gesundheitsforschung Berlin”)

1. Abstract

Title

Maternal and Newborn Safety profile of Progestogen use in **EARLY** Pregnancy (PEARLY).

Rationale and background

Progestogens are commonly prescribed to women for the indication of luteal phase support (LPS) during in vitro fertilization (IVF)/ assisted reproductive technology (ART) treatment, when presenting with early pregnancy bleeding or recurrent pregnancy loss. After more than 60 years on the market the available clinical and pharmacovigilance safety data suggest that dydrogesterone has a favorable benefit-risk profile in the approved indications. However, recent implications and isolated claims by individuals within the scientific community have raised some questions related to the safety of dydrogesterone. Establishing a scientifically sound pregnancy and newborn safety registry will enable high quality safety data on dydrogesterone to be collected.

Research question and objectives

The primary objective is to assess the rate of major malformations in fetuses and newborns by indication and by exposure to progestogens *in the first trimester of pregnancy* with focus on dydrogesterone versus non-dydrogesterone treatments. This study aims to accurately characterize and describe users of progestogens in early pregnancy including past gynecological and obstetric history, indication for progestogen use, type of progestogen use and detail of the course of pregnancy, birth outcome and newborn health. A comparison of live birth rates and rate of malformations in fetuses and newborns will be based on the indication area (recurrent pregnancy loss*, bleeding in early pregnancy** or IVF/ART) and the treatment (dydrogesterone, other progestogens, and other treatments***).

Study design

This multinational, prospective, active surveillance, registry study following two cohorts will include study participants who are pregnant and seeking any type of medical*** treatment, including dydrogesterone and other progestogens, for either (A) recurrent pregnancy loss* and/or bleeding in early pregnancy** or (B) as IVF/ART support. Pregnant women not taking progestogen and are advised an alternative non-medical treatment, in the context of bleeding in early pregnancy, recurrent pregnancy loss, or undergoing natural cycle frozen embryo transfer (NC-FET) can also be included in this study. Eligible study participants will be recruited via an international network of prescribing Health Care Practitioners (HCPs) in China, Turkey, and Russia with the aim to collect data related to maternal safety and newborn safety in women prescribed progestogens during early pregnancy. Study participants will be followed from early pregnancy until 6 – 12 weeks after giving birth. All malformations will be captured via direct contacts with the study participants. Study participants will be sent online questionnaires via the electronic Patient Reported Outcomes (ePRO) solution provided by MediData. Major malformations reported by the study participants will be validated by ZEG Berlin via relevant source documents and if necessary, via contacting the treating HCPs. The total study duration is planned for approximately 4 years including recruitment and follow-up.

Population

Pregnant women aged 18 to 35 who are treated with progestogens, including dydrogesterone, or other treatment for (A) recurrent pregnancy loss* and/or bleeding in early pregnancy** or as (B) IVF/ART support can be included in the study. Study participants are only recruited after the decision on treatment is made. Additionally, study participants will be recruited in different geographical areas in China, Turkey and Russia where dydrogesterone is marketed.

*habitual miscarriage / ** threatened miscarriage

*** Other treatments contain medical i.e., non-drug treatment plan (e.g. yoga, meditation, bed rest), pharmaceutical i.e., prescribed non-dydrogesterone based drug therapy including over-the-counter (OTC) and medicinal i.e., non-pharmaceutical including herbal, traditional medicines etc.

Variables

The primary variable of interest is the rate of major malformations in fetus and newborns. Data are collected on treatment, treatment indication, risk factors and potential confounding factors for malformations.

Data sources

Study data, information on risk factors and potential confounding factors, and information on malformations will be obtained from the study participants directly via ePRO. In case a potential major malformation is reported by the study participant, the reported event will be confirmed via review of medical documentation provided by the study participant or alternatively, obtained via the treating HCP.

Study size

Approximately 11,000 study participants (5,500 early pregnancy bleeding/recurrent pregnancy loss and 5,500 IVF/ART) will be recruited via a network of recruiting HCPs prescribing dydrogesterone or other treatment. Approximately 5,500 study participants per subcohort are statistically sufficient (assumptions: power = 90%, one-sided $\alpha = 0.025$, 20% drop-out rate, incidence proportion of 200 major malformations per 10,000 births) to exclude a 2.0-fold risk (Odds Ratio (OR)). The study is powered to test the non-inferiority of dydrogesterone treatment.

Data analysis

The primary analysis will focus on an “as treated” (AT) population analysis set whereby the outcomes of interest are assigned to the treatment exposure during the first trimester of pregnancy. The risk of major malformations will be assessed by unconditional logistic regression for each indication. Potential confounding or risk factors will be considered either in a pre-analysis step regarding cohort balancing using methods such as propensity scores, or by subsequent inclusion into the logistic model as cofactors for adjustment of the treatment effect. Crude and adjusted ORs and 95% confidence intervals (CI) will be estimated. The null hypothesis to be tested is: $(OR_{MM}) \geq 2.0$ (i.e., the malformation odds ratio for dydrogesterone vs. non-dydrogesterone is higher or equal to 2.0). The alternative hypothesis is defined as $OR_{MM} < 2.0$.

1 Amendments and updates

Number	Date	Section of study protocol	Amendment or update	Reason
V01-00	16-JUL-2021	NA	First version	
V02-00	11-OCT-2021	
 Section 3: Rationale and background Section 5.2.2.1 Inclusion criteria Section 5.7.3 Interim analyses 	Amendments as per recommendation by the Global Ethics Committee	

2 Milestones

Milestone	Planned date
Global Ethics Approval	September 2021
Registration in the EU PAS register	October 2021
Start of data collection (First Patient In)	December 2021
End of data collection (Last Patient Last Follow-Up)	April 2024
Study interim/progress report 1	March 2022
Study interim/progress report 2	December 2022
Study interim/progress report 3	September 2023
Data base lock	August 2024
Final report of study results	November 2024

3 Rationale and background

Progestogens are commonly prescribed to women for the indication of luteal phase support (LPS) during IVF (in vitro fertilization)/ART (assisted reproductive technology) treatment, when presenting with early pregnancy bleeding or recurrent pregnancy loss. While miscarriage is a frequent complication of early pregnancy (estimated to occur in 10–20% of pregnancies), recurrent miscarriage is less common, with prevalence estimates varying between 0.8% recurrent miscarriage is less common, with prevalence estimates varying between 0.8% and 3% [1]. Recommendations for treatment options for miscarriage differ between guidelines, largely a result of the guidelines being continually updated in line with the latest clinical evidence. In practice,

the onus is on the prescribing physician to ensure their practices are based on the most recently available data and local recommendations. After 60 years of availability on the market, the available clinical and post-marketing safety data have indicated that dydrogesterone has a favorable benefit-risk profile in the approved indications. However, recent implications and isolated claims by individuals within the scientific community [2–5] have raised some questions related to the safety of dydrogesterone, including a retrospective cohort study suggested an increased risk of major cardiac malformations in newborns exposed to dydrogesterone [3]. The study was methodologically flawed and has since been retracted by the publishing journal.

This registry study aims to establish a scientifically sound pregnancy and newborn safety data set to document any putative teratogenic risks upon exposure to progestogens. A large sample size registry with detailed characterization of participants' background, treatment and pregnancy outcome will provide generalizability and precision in addition to possible future regulatory requests from health authorities.

4 Research question and objectives

Congenital malformations are structural abnormalities of prenatal origin and can be classified into three groups based on their cause: genetic, environmental or multifactorial (e.g., twinning) [6]. Most congenital malformations (i.e., structural birth defects) result from abnormal development during embryogenesis [7]. The present study is being designed to assess maternal and newborn safety after progestogen exposure in early pregnancy. It aims to accurately characterize the demographic profile of users of progestogens in early pregnancy including past gynecological and obstetric history, indication for progestogen use (specific focus will be given to documenting use during IVF/ART and as treatment for bleeding in early pregnancy or recurrent pregnancy loss), type of progestogen and detail of the course of pregnancy, birth outcome and newborn health. A comparison of live birth rates and rate of malformations in fetus and newborn will be based on indication area and by treatment (dydrogesterone, other progestogens, or other treatment). In keeping with regulatory requirements, reportable adverse drug reactions will be relayed to the relevant marketing authorization holders (MAHs).

4.1 Primary Objectives:

- Assess the rate of major malformations in fetus and newborns by indication and by exposure to progestogens *during the first trimester of pregnancy*, with an emphasis on dydrogesterone versus non-dydrogesterone treatments.

4.2 Secondary Objectives:

- Describe the rate of other malformations by progestogen type and indication of use,
- To describe demographic, reproductive, and maternal health data, as well as available information on prenatal diagnostics and pregnancy outcome for the mother and the newborn.

4.3 Explorative Objectives:

- Characterize the hormonal and non-hormonal utilization patterns of dydrogesterone and non-dydrogesterone treatment in study participants and describe captured background risk scenarios which may serve as causal factors for major fetal and newborn malformations, not only limited to start and stop dates for all products taken during pregnancy, but also including duration, and indication,
- Describe the rate of (spontaneous) miscarriage,
- Describe the rate of induced abortions which may be attributed to maternal health or malformations in the fetus.

5 Research methods

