5.1 Study design

The PEARLY study is a prospective, observational, multi-center, multi-country, active surveillance registry study.

Different populations (based on different indications) will be included in the study with different subsequent analyses and separate data collection/follow-up for each of the cohorts of interest (see [Figure 1](#)). The different indication areas of interest include:

Cohort A: bleeding in early pregnancy/recurrent pregnancy loss

Cohort B: IVF/ART

A comparison of live birth rates and rate of major malformations in fetus and newborns will be based on indication area and by treatment (dydrogesterone, other progestogens, or other treatment).

[figure not shown]
Primary analyses focus on the rate of major malformations with exposure in the first trimester of pregnancy to:

- (1) Dydrogesterone versus non-dydrogesterone treatment

For the primary analysis, study participants taking any dydrogesterone preparation during the first trimester of pregnancy (at any time regardless of dosage and duration) as mono-treatment will be considered in the dydrogesterone group. Study participants taking at least one non-dydrogesterone preparation during the first trimester of pregnancy (at any time regardless of dosage and duration) as mono-treatment (i.e. no combination with dydrogesterone or another non-dydrogesterone) will be considered in the non-dydrogesterone group.

Further subgroups regarding specific dosage and duration will be considered in subgroup analyses.

Figure 1: Study Design

DYD: dydrogesterone, EDD: Estimated Date of Delivery, FU: follow-up, W: week, REOS: Regular End Of Study

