5.2.1 Selection of the Study Population

Study participants will be enrolled by recruiting HCPs. The recruiting HCPs are not necessarily involved in the subsequent follow-up (FU) of study participants. The recruiting HCP's role is to explain the nature of the study, its purpose and associated procedures, and the expected duration of follow-up for each study participant prior to their entry into the study.

Potential study participants will be identified by recruiting HCPs following initiation of progestogen or other treatment within the first trimester of pregnancy. Study participants will be recruited based on the inclusion and exclusion criteria as defined in section 5.2.2. Study population. As this is an observational registry study, the decision to prescribe dydrogesterone or other treatment is solely at the discretion of the HCP and the study participant. Study participants will continue to be managed throughout the study according to their HCP's prescribed treatment and will not be allocated to a study intervention.

Study participants will have the opportunity to ask questions and will be informed about their right to withdraw from the study at any time without disadvantage and without having to provide reasons for their decision. This information will be provided during the consenting process. Participation to the study is only possible if the informed consent and data privacy form is signed by the study participant. Once enrolled, a study participant may discontinue (and restart) treatment or may switch to another treatment as advised by the HCP at any time. However, study participants will continue to be followed whether or not they remain on the prescribed treatment, provided that they do not withdraw their consent.

Data will be collected directly from the study participants through electronic patient-reported outcome (ePRO) questionnaires. This means that study participants will be followed by ZEG Berlin independent of the HCP and follow-up is not necessarily linked to a clinical office visit. ZEG Berlin will obtain permission from the study participant to contact *any* treating or diagnosing HCP for clarification of a reported medical events (e.g. major malformations) during the study's observation time.

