5.7.2 Primary analysis

The primary analysis cohorts are defined as pregnant women using (I) dydrogesterone during the first trimester versus (II) other treatment and/or treatment combinations and/or no treatment during the first trimester as defined in section 5.1. Further analyses on subcohorts of (II) will be considered as secondary or sensitivity analyses. The safety conclusions regarding risk of major malformation will be based on the “as treated” (AT) population analysis set whereby outcomes of interest are assigned to the treatment used during the first trimester of pregnancy.

The overall incidence of major malformation will be calculated with respect to all pregnancies observed in the respective cohort and compared per indication area.

The null hypothesis is defined as odds ratio (OR) for major malformation $H_0: (OR_{MM}) \geq 2$ obtained from a comparison of the primary analysis cohorts. The alternative hypothesis is defined as $H_A: OR_{MM} < 2$, respectively.

The risk of major malformation as compared between treatment cohorts will be assessed by unconditional logistic regression. Potential factors of influence, potential confounding factors or risk factors, will be considered either in a pre-analysis step regarding cohort balancing using methods based on propensity scores, e.g., inverse probability of treatment weighting (IPTW) or by subsequent inclusion into the logistic model as cofactors for adjustment of the treatment effect. Crude and adjusted OR and 95% confidence intervals (CI) will be estimated.

All statistical details including derived variables content of tables and proposed format will be detailed in the SAP.

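### If the first-trimester as-treated grouping is also used for live birth and miscarriage, switching after enrolment can create group differences with no true effect

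*Protocol*

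**What the plan says.** **Grouping.** The Abstract (Data analysis) plans an as-treated primary analysis "whereby the outcomes of interest are assigned to the treatment exposure during the first trimester of pregnancy". Section 5.7.2 repeats this: "outcomes of interest are assigned to the treatment used during the first trimester of pregnancy". Section 5.1 places in the dydrogesterone group "study participants taking any dydrogesterone preparation during the first trimester of pregnancy (at any time regardless of dosage and duration) as mono-treatment".

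**Comparator.** Section 5.1 admits a woman on a non-dydrogesterone preparation only "as mono-treatment (i.e. no combination with dydrogesterone or another non-dydrogesterone) will be considered in the non-dydrogesterone group". Section 5.7.2 defines the comparator as "other treatment and/or treatment combinations and/or no treatment during the first trimester". The first leaves combinations out of both groups; the second puts them in the comparator.

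**Switching.** Women are recruited after treatment has been decided or started (sections 5.2.1 and 5.2.2). Section 5.2.1 then says: "Once enrolled, a study participant may discontinue (and restart) treatment or may switch to another treatment as advised by the HCP at any time". They remain in follow-up.

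**Outcomes.** Section 5.1 states: "A comparison of live birth rates and rate of major malformations in fetus and newborns will be based on indication area and by treatment". The Abstract and the opening of section 4 say the same in substance. Miscarriage is an explorative objective (section 4.3). Section 5.3.2.2 lists first-trimester progestogen intake and pregnancy outcome together among the variables for the secondary objective.

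**The concern.** Group membership depends on what happens after enrolment. A woman enrolled without a progestogen, which the inclusion criteria allow, who starts dydrogesterone some weeks later is a dydrogesterone mono-user under section 5.1. Her event-free weeks before the switch are credited to dydrogesterone. A woman on the same plan who miscarries before any switch stays in the reference. This is the familiar immortal-time mechanism.

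The path has no mirror image. A dydrogesterone user who stops and takes nothing else has still used it in the trimester and stays in the dydrogesterone group.

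Logistic regression on baseline covariates or IPTW, as planned in section 5.7.2, does not remove the problem, because the groups themselves use post-enrolment information. The bias list in section 5.9 does not mention it. What is at stake is a live-birth or miscarriage difference by treatment that reflects the grouping rule rather than the drug.

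**Working it through.** **Inputs.** The protocol gives no switch rate, no timing of losses and no expected live-birth rate, so there is no planned figure to reproduce. It does quote miscarriage in 10–20% of pregnancies (section 3).

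Assumptions: n = 1,000 women starting in each group, no treatment effect, total loss L = 15%, half of the losses before a single switch point, and a fraction s = 20% of surviving reference women switching, with later losses proportional.

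**Step 1: counts.**
- Losses per group: 1,000 × 0.15 = 150, of which 75 are early and 75 late.
- Alive at the switch point: 1,000 − 75 = 925.
- Switchers: 0.20 × 925 = 185.
- Later losses among switchers: 0.20 × 75 = 15.
- Reference women who do not switch: 1,000 − 185 = 815, with 150 − 15 = 135 losses.

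**Step 2: no-drug women who start dydrogesterone count as dydrogesterone (section 5.1).**
- Dydrogesterone: (150 + 15)/(1,000 + 185) = 165/1,185 = 13.9%.
- Reference: 135/815 = 16.6%.
- False loss risk ratio: 0.84. Live birth: 1,020/1,185 = 86.1% versus 680/815 = 83.4%.
- Over s = 10–30% and L = 10–20%, the risk ratio runs from 0.75 (s = 30%, L = 10%: 115/1,285 versus 85/715) to 0.92 (s = 10%, L = 20%: 210/1,090 versus 190/910).

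**Step 3: switches between drugs.** The result depends on who switches and on which section is followed.

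| Rule for switchers | Who switches (20% of survivors) | Loss, dydrogesterone vs reference | Risk ratio |
|---|---|---|---|
| Dropped from both groups (5.1) | Reference only | 150/1,000 vs 135/815 | 0.91 |
| Dropped from both groups (5.1) | Both groups equally | 135/815 vs 135/815 | 1.00 |
| Dropped from both groups (5.1) | Dydrogesterone only | 135/815 vs 150/1,000 | 1.10 |
| Put in the comparator (5.7.2) | Dydrogesterone only | 135/815 vs 165/1,185 | 1.19 |

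**Step 4: check with different timing.** This is a week-by-week null calculation with seven first-trimester weeks after enrolment, constant hazards, 15% loss and the 30:70 allocation of cohort A.
- Later starters counted as dydrogesterone: loss odds ratio 0.91, 0.84 and 0.72 when 5, 10 and 20% of comparator women start it. With 50:50 allocation: 0.94, 0.89 and 0.79.
- Switchers dropped: 1.00 with equal switching, 0.90 if 20% leave the reference and 5% leave dydrogesterone, 1.11 if reversed.
- Combinations in the comparator: 1.04, 1.09 and 1.20 at 5, 10 and 20% switching.
- Grouping by treatment at enrolment: 85.0% versus 85.0% live birth, odds ratio 1.00 at every switch rate tried.

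**Step 5: primary outcome.** Section 5.7.2 takes all observed pregnancies as the denominator. Suppose malformations are recorded at the protocol's 2%, and only in the surviving pregnancies of step 2.
- Dydrogesterone: 0.02 × 1,020 = 20.4 of 1,185.
- Reference: 0.02 × 680 = 13.6 of 815.
- Odds ratio: (20.4/1,164.6)/(13.6/801.4) = 1.03.

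The weekly calculation (cohort A) gives 1.01–1.07 for 5–20% switching and 10–20% loss, and 0.96–1.00 if combinations go to the comparator.

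**The case against.** **The rule is not written for these outcomes.** Section 5.1 defines the groups for the primary analysis, and section 5.7.2 ties the as-treated set to conclusions on major malformation. Live birth is not named in objectives 4.1–4.3, miscarriage is only to be described, and section 5.7.2 leaves derived variables to the SAP. This stands in part: carrying the rule over is an inference. It is a natural one, because section 5.3.2.2 pairs first-trimester intake with pregnancy outcome and no other grouping is stated for the promised comparison. Section 5.7.1 does mention analysis by time on drug, but too vaguely to settle how switchers are handled.

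**The direction is not fixed.** A reader might infer that dydrogesterone will look protective in general. The documents do not support that. Step 2 applies only to women on no other preparation. In cohort B, inclusion without a progestogen is limited to natural-cycle frozen embryo transfer, so the path is narrow there. Bed rest is itself listed as an other treatment, so one could argue that bed rest followed by dydrogesterone is not mono-treatment. For drug-to-drug switches the sign depends on relative switching and on the unresolved conflict between sections 5.1 and 5.7.2. All of this stands.

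**The primary analysis.** A reader might also infer that the malformation result is biased in favour of dydrogesterone. Step 5 shows a shift of a few percent, mostly the other way, against a margin of 2.0.

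**Conclusion.** The point holds as a conditional one. If live birth and miscarriage are compared with the first-trimester as-treated grouping, the rates can differ between groups with no true effect, and baseline adjustment does not correct this.

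For women who start on no drug and later take dydrogesterone, the bias favours dydrogesterone. The illustrative loss risk ratio is 0.84, with a range of 0.75–0.92 if 10–30% of all surviving reference women follow that path. For switches between drugs it can be nil, favourable or unfavourable. The primary malformation odds ratio is little affected.

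Switch rates and loss timing are assumptions throughout. The quoted 10–20% is a general miscarriage figure, not specific to either cohort. The size is therefore indicative; the mechanism and the conflict between sections 5.1 and 5.7.2 rest on the text.

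**What to change.** 1. In section 5.7.2, state that live birth and miscarriage are compared by the treatment in use or decided at enrolment, with switchers kept in their enrolment group. Section 5.3.2.4 already collects study treatment and treatment start at baseline.
2. Keep the as-treated first-trimester rule for major malformations, and prespecify the enrolment grouping as a sensitivity analysis.
3. Reconcile sections 5.1 and 5.7.2 on treatment combinations, and say whether a non-drug plan followed by dydrogesterone counts as mono-treatment.

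The cost is protocol and SAP wording and one extra grouping variable, with no new data. The downside is some dilution of the contrast if switching is common. Time-dependent exposure would be an alternative, but it needs switch dates: section 4.3 promises start and stop dates, whereas section 5.3.2.4 ticks treatment start and duration at baseline only.
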